# **Schematic of Study Design**

N = 34: Obtain informed consent from patients scheduled to undergo wrist arthroscopy at NYU Langone Health. Screen for inclusion and exclusion criteria; obtain history, document.

Perform diagnostic wrist arthroscopy with standard portals using NanoScope.

Perform NanoScope Assessment:

- 1. Diagnosis.
- 2. Intervention (intended).
- 3. Ease of use.
- 4. Diagnostic confidence.

Perform diagnostic wrist arthroscopy with standard portals using conventional instruments.

Perform Conventional Assessment:

- 1. Diagnosis.
- 2. Intervention.
- 3. Ease of use.
- 4. Diagnostic confidence.

### Final Assessments:

- 1. Compare diagnostic accuracy of NanoScope compared to conventional wrist arthroscopy instruments (gold standard).
  - a. Sensitivity
  - b. Specificity
- 2. Determine the rate of change in intervention.
- 3. Characterize surgeon-rated ease of use and surgeon-rated diagnostic confidence.
- 4. Determine the diagnostic correlation between pre-operative MRI and arthroscopy (NanoScope and conventional).

ept as authorized in writing by the study sponsor

Th Intervention

# 2 Introduction, Background Information and Scientific Rationale

### 2.1 Background Information and Relevant Literature

Arthroscopically assisted treatments continue to advance with regard to diagnostic efficacy and treatment capabilities. Arthroscopy affords surgical intervention through a minimally invasive approach, which translates into improved visualization, better outcomes, and decreased complications. Initially developed for larger joints such as the shoulder and knee, arthroscopic technology has advanced to include instrumentation amenable to accessing smaller joints, including the wrist. However, conventional instrumentation has inherent size limitations resulting in difficulty or inability to access smaller spaces (midcarpal joint, carpometacarpal joint, etc.). Innovations in instrumentation, including the Arthrex NanoScope, have focused on decreasing instrument size. The use of these smaller instruments have become commonplace for many surgeons for the diagnosis and treatment of wrist injuries. However, to our knowledge, there are no studies evaluating the diagnostic efficacy of these new arthroscopic visualization systems compared to conventional arthroscopic instruments.

The purpose of this study is to evaluate the diagnostic accuracy of the Arthrex NanoScope compared to conventional arthroscopic instruments. Additionally, we will analyze if there is difference in intended intervention, ease of use, and diagnostic confidence, and correlation between preoperative MRI and arthroscopic findings.

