### 4.2 Study Endpoints

### 4.2.1 Primary Study Endpoints

The primary endpoint will be diagnostic accuracy (%) compared to the gold standard of conventional wrist arthroscopy instruments.

The primary endpoint was chosen to determine if smaller instrumentation provides adequate visualization for the diagnosis of wrist pathology and can therefore be used as the sole means of evaluation.

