# 7.1 Study Procedures/Evaluations

### 7.1.1 Study Specific Procedures

- Patients undergoing wrist arthroscopy for diagnostic evaluation and treatment of a wrist injury will be enrolled pre-operatively following a
  discussion of the study, risks, benefits, and informed consent.
- All patients will be positioned supine and placed in an upper extremity traction tower with the shoulder abducted, elbow flexed to 90 degrees, forearm in neutral position.
- Standard arthroscopic portals will be made for viewing, instrumentation, inflow, and outflow: 3-4 portal, 6-R portal, midcarpal ulnar (MCU) portal, +/- midcarpal radial (MCR) portal, +/- 6-U portal.
- A diagnostic arthroscopy will be performed with the Arthrex NanoScope.
  - Structures evaluated:
    - Radial styloid
    - Proximal scaphoid articular cartilage
    - Scaphoid fossa
    - Radioscaphocapitate (RSC) ligament
    - Long radiolunate (LRL) ligament
    - Short radiolunate (SRL) ligament
    - Scapholunate (SL) ligament
    - Proximal lunate articular cartilage
    - Lunate fossa
    - Triangular fibrocartilage complex (TFCC)
  - The attending performing the diagnostic arthroscopy will make an initial diagnostic assessment based on the presence/location/severity of synovitis, articular cartilage integrity, ligament injury and determine the intended treatment.
- A diagnostic arthroscopy will then be performed with the standard arthroscopic instruments.
  - Structures evaluated:
    - Radial styloid
    - Proximal scaphoid articular cartilage
    - Scaphoid fossa
    - Radioscaphocapitate (RSC) ligament
    - Long radiolunate (LRL) ligament
    - Short radiolunate (SRL) ligament
    - Scapholunate (SL) ligament
    - Proximal lunate articular cartilage
    - Lunate fossa
    - Triangular fibrocartilage complex (TFCC)
  - The attending performing the diagnostic arthroscopy will make the final diagnostic assessment based on the presence/location/severity of synovitis, articular cartilage integrity, and ligament injury and determine the final treatment.

Study number: i20-00356 Page 17 Version: June 8, 2020

- Following the procedure the surgeon will perform a short questionnaire.
  - Surgeon rated visualization. (5 point scale)
  - Surgeon-rated ease of use. (5 point scale)
  - o Surgeon-rated diagnostic confidence. (5 point scale)
- The initial diagnostic assessment and final diagnostic assessment will be compared to determine diagnostic accuracy of the Arthrex NanoScope.

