# 10.2 Statistical Hypotheses

We hypothesize that there will be no difference in the diagnostic accuracy of the Arthrex NanoScope compared to conventional arthroscopic instruments.

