### 10.3.2 Analysis of the Primary Efficacy Endpoint(s)

### **Primary**

1. Diagnostic accuracy of Nanoscope compared to conventional arthroscope.

Diagnostic accuracy of the Arthrex Nanoscope will be described as a incidence/percentage compared to the diagnosis determined by wrist arthroscopy with conventional instruments.

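### The conventional scope is both comparator and reference standard, so the trial measures agreement with it and cannot test whether the two scopes are equally accurate

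*Combined protocol and SAP*

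**What the plan says.** The reference is fixed in several places.

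- Section 4.2.1: "The primary endpoint will be diagnostic accuracy (%) compared to the gold standard of conventional wrist arthroscopy instruments".
- Schematic of Study Design, Final Assessments: "Compare diagnostic accuracy of NanoScope compared to conventional wrist arthroscopy instruments (gold standard", with sensitivity and specificity listed beneath. Section 4.1 uses the same label.
- Section 7.1.1: "The initial diagnostic assessment and final diagnostic assessment will be compared to determine diagnostic accuracy of the Arthrex NanoScope". The initial assessment is the NanoScope one and the final assessment is the conventional one.
- Section 10.3.2: the result is a percentage "compared to the diagnosis determined by wrist arthroscopy with conventional instruments".

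The hypothesis in Section 10.2, repeated in Section 10.4, is comparative: "We hypothesize that there will be no difference in the diagnostic accuracy of the Arthrex NanoScope compared to conventional arthroscopic instruments".

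Two places show that the reference is not thought to be perfect. Section 2.1 says that "conventional instrumentation has inherent size limitations resulting in difficulty or inability to access smaller spaces". Section 10.4 takes the sensitivity of arthroscopy as .90, without saying which scope or which truth this refers to.

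The plan describes no third reference, no adjudication and no rule for findings on which the scopes disagree. One attending performs both examinations, NanoScope first (Sections 6.3.2 and 7.1.1), without blinding (Section 10.5.2).

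**The concern.** A test cannot serve as the yardstick and also be compared with another test on accuracy. Judged against itself, the conventional scope is never wrong, so the comparison in Section 10.2 has only one side that can vary.

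If the reference misses a lesion that the NanoScope shows, the planned scoring can only call that finding a NanoScope false positive. Section 4.2.1 says the endpoint should inform whether the smaller scope could be used on its own. For that question the two kinds of disagreement mean different things. A lesion found only by the conventional scope argues against sole use; a lesion found only by the NanoScope may not. The single percentage in Section 10.3.2 adds them together.

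**Working it through.** **Inputs.** N = 34, 31 with injury, prevalence 90%, and sensitivities .70 and .90 all come from Section 10.4. Reference sensitivities of .95 and .80, and a per-structure prevalence of 30%, are assumptions; the documents give no figures for them.

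**1. The plan's own figure.** A one-sample exact binomial test of .70 against .90 with n = 31 and at most 0.025 per tail rejects at 27 or more, or at 16 or fewer. This gives alpha 0.0478 and power 0.8068, matching the copied table row (0.048, 0.807, N1 = 31). 31/0.90 = 34.4, and the table gives 34. The calculation reproduces, but it takes injury status as known without error and compares one proportion with a fixed value. It has no term for an imperfect reference and no second scope. (The alpha of 0.95 and power of 0.819 printed in Section 10.4 are not those of this row; that is a separate matter.)

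**2. What the comparison can show.** Let a = both positive, b = NanoScope-only, c = conventional-only, d = both negative.

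- NanoScope accuracy = (a + d)/N.
- Conventional accuracy against itself = N/N = 100%.
- Difference = −(b + c)/N.

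The difference is never above zero, and it is zero only if the scopes agree in every case. It is the disagreement rate with a minus sign.

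**3. What reference misses would do.** Assume an error-free NanoScope, a perfectly specific reference of sensitivity s, and independent assessments. Let p be prevalence.

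- True lesions scored as NanoScope false positives = N × p × (1 − s).
- Apparent specificity = (1 − p)/[(1 − p) + p(1 − s)].
- Apparent accuracy = 1 − p(1 − s).

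One yes/no diagnosis per patient, p = 0.90, N = 34, hence 34 × 0.10 = 3.4 true negatives:

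| s | Scored as false positives | Apparent specificity | Apparent accuracy |
|---|---|---|---|
| 1.00 | 0 | 100% | 100% |
| .95 | 34 × .9 × .05 = 1.53 | 3.4/4.93 = 69% | 95.5% |
| .90 | 34 × .9 × .10 = 3.06 | 3.4/6.46 = 53% | 91% |
| .80 | 34 × .9 × .20 = 6.12 | 3.4/9.52 = 36% | 82% |

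Per structure, p = 0.30 (assumed): specificity is .7/.715 = 98%, .7/.73 = 96% and .7/.76 = 92% for s = .95, .90 and .80.

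**4. Why the net direction is open.** Let both scopes have sensitivity .90 and perfect specificity, at p = 0.90. True NanoScope accuracy is .9 × .9 + .1 = 91%. With independent assessments, both positive is .9 × .9 × .9 = .729 and both negative is .9 × .1 × .1 + .1 = .109, so apparent accuracy is 83.8%. If the surgeon instead carries every NanoScope finding into the final diagnosis, the two records are identical and apparent accuracy is 100%. The same true 91% can therefore appear too low or too high.

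**The case against.** The strongest reply is that comparing a new test with established practice is ordinary, and that falling short of a reference is a property of every index test. That is fair for a study of agreement. It does not rescue a hypothesis about the relative accuracy of the two scopes.

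Several stronger readings are tempting, and the documents do not support them.

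- *That the reference fails on the structures being scored.* Section 2.1 says "conventional instrumentation has inherent size limitations resulting in difficulty or inability to access smaller spaces (midcarpal joint, carpometacarpal joint, etc", and none of the ten structures listed in Section 7.1.1 is named as lying in those joints. The portals are "3-4 portal, 6-R portal, midcarpal ulnar (MCU) portal, +/- midcarpal radial (MCR) portal, +/- 6-U portal", so the conventional examination also has a midcarpal portal. The access limit bites mainly if diagnoses outside the list are scored, which the plan does not settle. The scoring problem still applies to any lesion the reference misses, for whatever reason.
- *That a structure the conventional scope could not see is recorded as normal.* No section says so. The data form is not in the documents, and Section 10.1 defers a formal SAP. What can be said is that no rule is stated.
- *That the NanoScope's results are biased downward.* The unblinded second look by the same surgeon works the other way, as step 4 shows.
- *That the direction of disagreement is lost altogether.* The Protocol Summary and the schematic name sensitivity and specificity, which partly separate the two kinds, and Section 10.3.7 lists individual data. But specificity still labels every NanoScope-only finding as an error.

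It is also true that much of the fragility of patient-level specificity comes from having about three negative patients. With three, any single extra finding moves it from 3/3 to 2/3. An extra lesion in a patient already positive changes nothing at that level.

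**Conclusion.** The point holds. That the conventional scope scores 100% by construction, and that Section 10.2 is therefore untestable, follows from the definitions and needs no numerical assumption. What the trial can estimate is agreement with conventional arthroscopy.

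The size of any distortion cannot be fixed from the documents. It depends on the reference's true sensitivity, on how independent the two assessments are, and on the unit of analysis, which is not stated. Under the step 3 assumptions, the apparent specificity of an error-free NanoScope is 36% to 69% with one diagnosis per patient at the planned prevalence, and 92% to 98% per structure at an assumed 30%. These are illustrations, not predictions. A reader might infer that the trial will understate the NanoScope. That is not established, because carry-over by the same surgeon could produce the opposite.

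**What to change.** 1. Reword Sections 10.2 and 10.4 and the primary endpoint as agreement with conventional arthroscopy, reported as positive and negative percent agreement, and state the unit of analysis. The numbers equal sensitivity and specificity against the conventional scope, but the label no longer claims that the conventional scope is always right.
2. Add a per-structure table of discordant findings by direction: NanoScope-only and conventional-only. Rest any conclusion about using the NanoScope on its own mainly on the conventional-only findings.
3. If the form does not already do so, record 'not visualised' separately from 'normal' for each structure and each scope, and do not count a conventional 'not visualised' as reference-negative.

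The cost is one response option and one table, with no added patients or procedures. The analysis changes can go into the formal SAP that Section 10.1 still promises; the form change has to be in place before data are collected. The downside is a more modest claim, agreement instead of accuracy. These steps do not show which scope is right when they differ, and they do not remove carry-over between the two assessments.

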### 2.2 Name and Description of the Investigational Agent

The Arthrex NanoScope is commonly used for joint arthroscopy. The instrument itself is not an investigational agent. We are evaluating the instruments diagnostic accuracy compared to conventional instruments.

Study number: i20-00356 Page 11 Version: June 8, 2020

The FDA-cleared Arthrex NanoScope System is intended to be used as an endoscopic video camera in a variety of endoscopic surgical procedures, including but not limited to: orthopedic, laparoscopic, urologic, sinuscopic, and plastic surgical procedures. The device is also intended to be used as an accessory for microscopic surgery.

Instrument: Arthrex NanoScope - Nano Operative Arthroscopy System

1.9 mm single-use, needle-size sterile camera.

- 13" medical grade 3-in-1 camera control unit.
- This device is currently in use for wrist arthroscopy. The intended purpose of this research study is to compare this devices diagnostic accuracy to conventional larger arthroscopic equipment.
- https://www.arthrex.com/hand-wrist/nano-arthroscopy-system-for-hand-and-wrist

### 2.3 Rationale

The use of these smaller arthroscopic instruments have become commonplace for many surgeons for the diagnosis and treatment of wrist injuries. However, to our knowledge, there are no studies evaluating the diagnostic efficacy of these new arthroscopic visualization systems compared to conventional arthroscopic instruments. The purpose of this study is to evaluate the diagnostic accuracy of the Arthrex Nanoscope compared to conventional arthroscopic instruments. Additionally, we will analyze if there is difference in intended intervention, ease of use, and diagnostic confidence.

### 2.4 Potential Risks & Benefits

### 2.4.1 Known Potential Risks

There are no additional potential risks pertaining to this study involving with the use of the Arthrex NanoScope compared to conventional wrist arthroscopy instruments. The NanoScope will be used with the standard extremity stabilization tower and arthroscopic portals as are used with conventional instruments. The diagnostic arthroscopy using the NanoScope will be performed immediately prior to the diagnostic arthroscopy with the conventional instrumentation. Estimated additional time to perform the diagnostic arthroscopy with the NanoScope is < 5 minutes, which will not result in subjects exposure to risks associated with prolonged anesthesia or surgery. There is also no additional wrist of passing a second device (NanoScope) into the wrist joint, in addition to the conventional arthroscope.

### 2.4.2 Known Potential Benefits

There are no potential benefits to the participants of this study by virtue of participation.

Version: June 8, 2020

# 3 Objectives and Purpose

# 3.1 Primary Objective

To evaluate the diagnostic accuracy of the Arthrex NanoScope compared to conventional arthroscopic instruments.

### 3.2 Secondary Objectives (if applicable)

To determine if the diagnostic accuracy of the Arthrex NanoScope compared to conventional arthroscopic instruments results in a change in intended intervention.

To determine the surgeon-rated ease of use and diagnostic confidence of the Arthrex NanoScope.

To determine the diagnostic correlation between pre-operative MRI and arthroscopy (NanoScope and conventional). The MRI is standard of care for evaluation of ligamentous wrist pathology. It will not be mandated as part of the protocol.

# 4 Study Design and Endpoints

### 4.1 Description of Study Design

- Prospective cohort study, Diagnostic
- Single cohort
  - Step 1: NanoScope
  - Step 2: Conventional wrist arthroscopy instruments
  - A single cohort study, comparing the diagnostic accuracy of the Arthrex NanoScope to conventional instruments (gold standard).
- Single center
- Instrument: Arthrex NanoScope

### 4.2 Study Endpoints

### 4.2.1 Primary Study Endpoints

The primary endpoint will be diagnostic accuracy (%) compared to the gold standard of conventional wrist arthroscopy instruments.

The primary endpoint was chosen to determine if smaller instrumentation provides adequate visualization for the diagnosis of wrist pathology and can therefore be used as the sole means of evaluation.

### 4.2.2 Secondary Study Endpoints

Version: June 8, 2020

Secondary endpoints will be a incidence of change in intended intervention and surgeon-rated ease of use and diagnostic confidence.

These secondary endpoints were chosen to determine if a difference in diagnostic accuracy results in a change in intervention as well as to determine the number of uses required for surgeon familiarity with the instruments.

### 4.2.3 Exploratory Endpoints

An exploratory end point will be evaluation of diagnostic accuracy relative to surgeon-rated ease of use and diagnostic confidence to determine if there is a learning curve.

# 5 Study Enrollment and Withdrawal

### 5.1 Inclusion Criteria

In order to be eligible to participate in this study, an individual must meet all of the following criteria:

- 1. Age > 18 years.
- 2. Wrist pathology based on clinical examination/imaging studies undergoing wrist arthroscopy for further evaluation/treatment.
- 3. Willingness to participate in the study

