Number of participants	34
Description of Study Agent/Procedure	The Arthrex NanoScope is a 1.9 mm wrist arthroscopy system.
Reference Therapy	Conventional wrist arthroscope
Key Procedures	Diagnostic wrist arthroscopy of wrists with clinical and imaging confirmation of internal derangement (ligament/articular/bony injury).
Statistical Analysis	Descriptive statistics will be used to provide a quantitative summary of the data in the study. Specifically, the analysis performed included measures of central tendency (mean, median, and mode) and measures of variability (range and standard deviation). Categorical data will be described in percentages and a Chi-squared test will be employed to detect if these categorical variables are related between the two treatment groups with a p value of < .05. Continuous data will be described in means with standard deviations. A two-tailed Student's T-test will be employed to compare the means between the two treatment groups with a p value of < .05.

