### 5.6 Total Number of Participants and Sites

Recruitment will end when approximately 34 participants are enrolled. It is expected that approximately 34 participants will be enrolled in order to produce 34 evaluable participants. Participants will be enrolled at four 4 NYU study sites:

- 1. NYU Langone Orthopedic Hospital
- 2. Tisch Hospital, NYU Langone Health
- 3. NYU Langone Orthopedic Center (38th Street)
- 4. Joan H. & Preston Robert Tisch Center at Essex Crossing, NYU Langone Health

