### 10.4 Sample Size

34 participants will be recruited to meet a goal of evaluable participants for the study.

- Outcome measure: diagnostic accuracy
- Test statistic: descriptive statistics

Study number: i20-00356 Page 25 Version: June 8, 2020

• Null hypothesis: We hypothesize that there will be no difference in the diagnostic accuracy of the Arthrex NanoScope compared to conventional arthroscopic instruments.

• Type I error rate (alpha): 0.95

Power level: 0.819

Dropout: Not applicable.

• Approach to handling withdrawals and protocol violations: Not applicable.

Statistical method used to calculate the sample size: At 90% prevalence, in order to detect a change in sensitivity (true-positive) between .70 (sensitivity of MRI) and .90 (sensitivity of arthroscopy), we would need a minimum of 34 subjects with a minimum of 31 who had a ligamentous wrist injury (see table below). This was determine with the guidance of the Center for Clinical Research.

Mohamad Adam Bujang and Tassha Hilda Adnan, Requirements for Minimum Sample Size for Sensitivity and Specificity Analysis

www.jcdr.net

H a 0.60 0.70 0.80 0.90 0.70 0.80 0.90 0.90 0.90 0.90 0.95 0.60 0.70 0.80	Power 0.804 0.810 0.804 0.889 0.801 0.826 0.885 0.818 0.807 0.819 0.816 0.804 0.804	p-value 0.047 0.044 0.041 0.039 0.048 0.034 0.035 0.044 0.048 0.040 0.048	N1 199 49 20 12 181 45 19 155 31 107 231 199	N 284 70 29 17 259 64 27 221 44 153 330		Perv 70% 70% 70% 70% 70% 70% 70% 70% 70% 70%	H o 0.50 0.50 0.50 0.50 0.60 0.60 0.60 0.70	H a 0.60 0.70 0.80 0.90 0.70 0.80 0.90 0.80 0.90	0.804 0.810 0.804 0.889 0.801 0.826 0.885 0.818	p-value 0.047 0.044 0.041 0.039 0.048 0.034 0.035 0.044	N1 464 114 47 28 422 105 44 362	N 663 163 67 40 603 150 63 517
0.70 0.80 0.90 0.70 0.80 0.90 0.90 0.90 0.95 0.60	0.810 0.804 0.889 0.801 0.826 0.885 0.818 0.807 0.819 0.816 0.804 0.804	0.044 0.041 0.039 0.048 0.034 0.035 0.044 0.048 0.040 0.048 0.047	49 20 12 181 45 19 155 31 107 231	70 29 17 259 64 27 221 44 153 330		70% 70% 70% 70% 70% 70% 70% 70%	0.50 0.50 0.50 0.60 0.60 0.60 0.70	0.70 0.80 0.90 0.70 0.80 0.90	0.810 0.804 0.889 0.801 0.826 0.885 0.818	0.044 0.041 0.039 0.048 0.034 0.035	114 47 28 422 105 44 362	163 67 40 603 150 63

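### Section 10.4 needs 31 ligament-injured wrists among 34 enrolled, on an unsourced 90% prevalence, and neither the entry criteria nor the recruitment stop secures that number

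*Combined protocol and SAP*

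**What the plan says.** Section 10.4 (Sample Size) sets out the planning assumption: "At 90% prevalence, in order to detect a change in sensitivity (true-positive) between .70 (sensitivity of MRI) and .90 (sensitivity of arthroscopy". From this it concludes that "we would need a minimum of 34 subjects with a minimum of 31 who had a ligamentous wrist injury". The condition counted for sensitivity is thus ligamentous injury, and at most 3 of the 34 wrists may lack it. The same section gives "Power level: 0.819" and makes no allowance for dropout.

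Section 5.1 (Inclusion Criteria), item 2, reads "Wrist pathology based on clinical examination/imaging studies undergoing wrist arthroscopy for further evaluation/treatment". The only exclusion criterion in 5.2 is age. The Key Procedures row of the Protocol Summary describes the wrists studied as having "internal derangement (ligament/articular/bony injury" among its terms. Section 7.1.1 has the surgeon assess synovitis and cartilage as well as ligaments.

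Section 5.6 says "Recruitment will end when approximately 34 participants are enrolled" and expects those 34 to yield 34 evaluable participants. No section ties the end of recruitment to the number of injured wrists, and none gives a source for the 90%.

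**The concern.** The number of wrists with the condition is the denominator for sensitivity, which the Protocol Summary names in the primary outcome. Section 10.4 states a minimum for that denominator, but the plan contains neither evidence that 34 consecutive enrolments will supply it nor a rule that makes them do so. A patient with isolated cartilage damage or synovitis meets criterion 2, takes one of the 34 places and does not count toward the 31.

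At stake is whether the size and power printed in 10.4 are what the design delivers. A reader would take from 10.4 that 34 participants bring 31 injured wrists and a power of about 0.8. If fewer injured wrists are found, the sensitivity estimate is less precise than planned and the stated power does not apply.

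**Working it through.** **Inputs.** From 10.4: prevalence 0.90, null sensitivity 0.70, alternative 0.90, N = 34, N1 = 31. The table row in 10.4 for 0.70 against 0.90 gives power 0.807, p-value 0.048 and N1 = 31, with N = 34 at 90% prevalence, 39 at 80% and 44 at 70%. The documents give no prevalence other than 90% for this population. The 80% and 70% used below are assumptions, chosen because the plan's own table lists them.

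**Step 1: reproduce the plan's figure.** Take a one-sample exact binomial test, two-sided with 0.025 in each tail, and n = 31. Reject if X ≤ 16 or X ≥ 27. The actual type I error at 0.70 is 0.0478 and the power at 0.90 is 0.8068, which match the row's 0.048 and 0.807. Sidedness is not stated and is inferred from this match. The required total is N = 31/0.90 = 34.4, which the table rounds down to 34.

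The 0.819 printed in the text is the table's value for 0.80 against 0.90 (N1 = 107, N = 119 at 90% prevalence), not for the contrast used. The stated "Type I error rate (alpha): 0.95" cannot be a type I error rate; the table row corresponds to a nominal 0.05. Both are separate slips and do not drive what follows.

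**Step 2: injured wrists among 34.** Let K be the number injured, K ~ Binomial(34, p). The expected count is 34p, and the chance of meeting the minimum is P(K ≥ 31).

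**Step 3: power averaged over K.** Averaged power = Σ P(K = k) × power(k), where power(k) is the exact two-sided power at n = k. At p = 0.90 the main terms are:

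| k | P(K = k) | power(k) | product |
|---|---|---|---|
| 27 | 0.031 | 0.718 | 0.022 |
| 28 | 0.070 | 0.695 | 0.049 |
| 29 | 0.131 | 0.671 | 0.088 |
| 30 | 0.197 | 0.647 | 0.127 |
| 31 | 0.228 | 0.807 | 0.184 |
| 32 | 0.193 | 0.789 | 0.152 |
| 33 | 0.105 | 0.770 | 0.081 |
| 34 | 0.028 | 0.750 | 0.021 |

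These products sum to 0.724. Counts of 26 or fewer add about 0.009, giving 0.733. Exact power does not rise steadily with n, and 31 is a local peak, so both smaller and larger counts in this table have power below 0.807.

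**Step 4: results with N fixed at 34.**

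| Prevalence | Expected injured | P(K ≥ 31) | Averaged power | N in the plan's table |
|---|---|---|---|---|
| 90% (plan) | 30.6 | 0.554 | 0.73 | 34 |
| 80% (assumed) | 27.2 | 0.070 | 0.64 | 39 |
| 70% (assumed) | 23.8 | 0.003 | 0.55 | 44 |

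**The case against.** A reader might infer that the enrolled population is not the one 10.4 describes, or that the 31 will probably be missed because criterion 2 is too broad. The documents do not support either reading. A 90% prevalence already presupposes some wrists without ligament injury, so a broad entry rule does not contradict it. No section reports the sites' case mix. The Key Procedures wording is a description rather than an eligibility rule, and wrists with ligament injury alongside other findings would count toward the 31. At the plan's own 90%, reaching 31 is slightly more likely than not. The 45% chance of falling short there comes from rounding 34.4 down to 34 and from sampling variation, not from criterion 2. All of this stands, and it limits the point to a figure that is unsupported and unsecured.

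It can also be said that the narrow wording in 10.4 is the outlier, since the endpoint in 4.2.1 and the assessment in 7.1.1 concern wrist pathology generally. That is fair, and it is a reason to correct 10.4 rather than 5.1.

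Finally, the primary analysis in 10.3.2 is descriptive and no test of sensitivity against 0.70 is specified, so lost power may seem moot. The practical loss is indeed modest. With a sensitivity of 0.90, the 95% half-width 1.96 × √(0.9 × 0.1/n) is 10.6 percentage points at n = 31, 11.3 at 27 and 12.0 at 24. The 0.70 against 0.90 contrast is also MRI against arthroscopy rather than NanoScope against the conventional scope, and correcting the prevalence does not change that. Still, 10.4 prints a power and a minimum count, and these should be figures the design can deliver.

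**Conclusion.** The point holds as a defect in the sample-size statement. The minimum of 31 rests on an unsourced 90%, and neither eligibility nor the recruitment stop secures it. On the plan's own assumption, 34 enrolled gives 30.6 injured wrists on average, a 55% chance of meeting the minimum and an averaged power of about 0.73, against 0.807 in the table row and 0.819 in the text. At an assumed 80% or 70% the expected count falls to about 27 or 24, the chance of reaching 31 to 7% or 0.3%, and averaged power to about 0.64 or 0.55.

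These figures assume that participants are independent draws with a common prevalence, that the two-sided exact test reproduced from the table is the intended one, and that all 34 are evaluable, as 5.6 expects. They do not show that the true prevalence is below 90%. The consequence is an overstated planning figure that should be corrected; it does not invalidate the study.

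**What to change.** Keep criterion 2 and N = 34, and amend 10.4 only:

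- Stop presenting 31 injured wrists as what 34 enrolled will supply.
- Give the basis for the 90%, for example the sites' own arthroscopy case mix, or say that it is an assumption.
- State the expected injured number (about 24 to 31) and the matching averaged power (about 0.55 to 0.73) over an assumed 70-90% prevalence.

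The cost is wording and a less favourable stated figure; no further participants are needed.

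Narrowing criterion 2 to suspected ligament injury is not advised. Specificity is also part of the primary outcome, and at 90% prevalence only about 34 − 30.6 = 3.4 wrists are available for it. A narrower entry rule would shrink that number further and restrict an assessment that deliberately covers articular surfaces. It would still not guarantee 31 injuries confirmed at arthroscopy.
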